## 12.5 Retention and Compliance

Drop-outs are a difficult problem and one that is best handled proactively rather than retrospectively. We will make a concerted effort to minimize the number of drop-outs, beginning with the participants who are accrued. If a participant seems unwilling to participate or indicates that they may not be able to be compliant, we will not press them to participate. In addition, participants who refuse treatment at some point during the course of therapy will be encouraged to stay in the study and provide outcome data. Despite our best efforts, some data will be missing due to missed visits or participants refusing further participation. We propose to analyze the data using SAS Proc Mixed, a program that provides several computational methods for obtaining maximum likelihood estimates for repeated measures problems, allows for unbalanced designs, missing data at some times, structured or unstructured covariance matrices, and growth curve parameterizations of time effects. Additionally, we will employ multiple imputation methods to assess the treatment effect on the outcomes using the SAS multiple imputation procedures. Both the mixed models and imputation analyses assume participants are missing at random, that is, the missingness can depend on covariates and observed outcomes but not the missing outcomes.

This assumption that the missingness does not depend on the missing data cannot be tested completely since the data needed to test the assumption are missing. However, we will use logistic regression to see if we can determine which covariates, if any, are related to missingness, and these covariates will be used to create a propensity-to-be-missing score which will be used to generate a stratified analysis as described by Baker et al. Additionally, exploratory analyses using multiple imputations will assess the treatment effect over a range of assumptions regarding the missingness, allowing us to assess the sensitivity of our assumptions.

Compliance is defined as the number of pills consumed over the course of the trial divided by the ideal number that should have been consumed over that period. It will be calculated based on the patient's self-reported pill diaries. The primary analyses will be intent to treat, estimating treatment efficacy will include all randomized participants, regardless of compliance. Additional per protocol exploratory analyses will assess the treatment effect in those patients who were at least 75% compliant.

## **12.6 Reporting and Exclusions**

Descriptive reports will consist of summary statistics (means, standard deviations, proportions, etc.) for participant characteristics and outcome measures by treatment arm, actual versus projected accrual, participation by the various NCORP sites, quality control information (retention, missing data, etc.), and a summary of toxicities and adverse events. Tables, graphs, and charts will be used to illustrate the data when appropriate. These reports will be prepared and presented to the WF DSMB committee every six months.

## **12.7 Evaluation of Toxicity**

### **Evaluation of Toxicity and Adverse Effects of Ramipril**

All patients will be evaluable for toxicity from the time of their first treatment with Ramipril. Toxicities will be quantified using the CTCAE v5.0 for Toxicity and Adverse Event Reporting. Fisher exact tests will be used to assess treatment differences in the incidence of individual toxicities, and logistic regression will be used to assess treatment differences in the incidence of any grade 3 or higher toxicity possibly, probably or likely related to Ramipril adjusting for baseline patient characteristics. In order to rule out cytoprotection of tumor by Ramipril, response rates will be compared to historical controls from RTOG 0825.

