## **4. PARTICIPANT SELECTION**

### **4.1 Inclusion Criteria**

- 4.1.1** Histologically proven diagnosis of glioblastoma or gliosarcoma (WHO grade IV) obtained at the time of a partial or gross total resection of the tumor. Patients who undergo a stereotactic needle biopsy alone are not eligible.
- 4.1.2** The tumor must have a supratentorial component.
- 4.1.3** History/physical examination within 14 days prior to enrollment
- 4.1.4** The patient must have recovered from the effects of surgery, postoperative infection, and other complications before enrollment.
- 4.1.5** Patient planning to receive brain RT, and concurrent and adjuvant temozolomide chemotherapy for 6 weeks as per standard of care therapy. Use of the Optune® (also known as Tumor Treating Fields or TTFields) device is allowed at provider discretion, but must begin after the Month 1 Post RT (10 wk) Neurocognitive-PRO assessment.
- 4.1.6** Study drug (Ramipril) must be given  $\geq 21$  days and  $\leq 42$  days after surgery.
- 4.1.7** All available brain MRI or CT imaging reports from surgery to study completion must be submitted. This includes any post-operative or pre-radiation scan reports.
- 4.1.8** ECOG 0, 1 or 2;
- 4.1.9** Age  $\geq 18$ ;
- 4.1.10** CBC/differential obtained within 14 days prior to enrollment, with adequate bone marrow function defined as follows:
  - Absolute neutrophil count (ANC)  $\geq 1,500$  cells/mm^3;
  - Platelets  $\geq 100,000$  cells/mm^3;
  - Hemoglobin  $\geq 10.0$  g/dl (Note: The use of transfusion or other intervention to achieve Hgb  $\geq 10.0$  g/dl is acceptable.)
- 4.1.11** Adequate renal function, as defined below:
  - BUN  $\leq 30$  mg/dl within 14 days prior to enrollment.
  - Creatinine  $\leq 1.7$  mg/dl within 14 days prior to enrollment.
- 4.1.12** Adequate hepatic function, as defined below:
  - Total Bilirubin  $\leq 2.0$  mg/dl within 14 days prior to enrollment.
  - ALT/AST  $\leq 3$  x normal range within 14 days prior to enrollment.

- 4.1.13** Patient must provide study specific informed consent prior to study entry.

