MRI/CT Brain: MRI Brain will be completed per standard of care at each study site. Sites are asked to provide MRI final reports with the specific visit form. As per section 4.1.7, patients who are unable to undergo MRI scanning should have CT brain scans done as per this schedule. Treating physician assessment of tumor response – i.e. response, progression or stable disease – will be captured for each completed imaging study.

Toxicity Assessments: Assessments by the study team will be done from Week 1 of RT and the start of Ramipril to 5-month post RT (end of study). This time period includes 30 days after treatment with Ramipril. Refer to section 6.2 for reported adverse events and risks when taking Ramipril.

Adverse Event Reporting: Refer to Section 10 of the protocol for specifics.

**Medication Diary:** Each patient is asked to fill in a Ramipril Medication diary and return it to the study team weekly during radiation therapy (weeks 1-6), and monthly on 1- and 4- month post RT visit. Since 2- and 3- month visits can be phone calls, the patient will need to mail back these diaries to the study team. Refer to Appendix D for a Ramipril Medication diary.

**Pill Count:** Patients will be asked to bring pill bottles to visit. Study team will count and record pills given, remaining and taken on the visit CRF.

**Ramipril Administration:** This study drug will be provided at no charge to patients for oral administration daily from Week 1 RT to post 4-month RT (Week 22). Study team will be required to order, distribute and inventory study drug. Refer to Sections 6.3 – 6.8 and for titration schedule 5.1.2 for details.

**Chemoradiation Summary:** At the RT Completion (Week 6) visit, a summary of the standard of care chemotherapy and radiation therapy will be gathered.

**Off Agent:** Use this form when a patient goes Off Agent either at the completion of study drug administration per protocol or at the time of early discontinuation. All study assessment should be continue to be completed, unless the patient is unwilling or withdraws consent. LabCorp samples do not need to be collected after the patient is Off Agent. Please use local labs to complete assessment information in REDCap.

**Off Study:** Use this form when a patient goes Off Study by either withdrawing consent or completing the study. This form serves as a way to track the patient status.

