#### Reasons for Not Reporting All Adverse Events

- Ramipril is a widely used medication taken routinely for high blood pressure on an outpatient basis. Side effects are well documented.
- Because Ramipril is widely used and its toxicity profile is well established, we feel the likelihood of Ramipril increasing standard treatment-related toxicities is low. By not collecting all AEs, we hope to expend our efforts in identifying toxicities that are unexpected and related to Ramipril.

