# **12. STATISTICAL CONSIDERATIONS**

## **12.1 Study Design/Description**

### **Study Design/Endpoints/Hypotheses**

We propose a single arm pilot study to assess the feasibility of the use of Ramipril for GBM and the effect of Ramipril on neurocognitive function in patients using Ramipril in addition to standard chemotherapy and RT for GBM. Patients will receive once daily oral Ramipril to be taken at the start of RT and continue for four months after completion of RT. Outcome assessments will be made at 1- and 4-month post-RT. The results of our trial will be compared to those from the control group of RTOG 0825. The objectives for this trial are: 1) to assess the retention rate of patients at 10 weeks of Ramipril treatment (6 weeks during RT and 4 weeks post RT) defined by compliance with drug therapy for at least 75% of doses during the 10 week period and completion of the composite neurocognitive battery, 2) to estimate the effect of 10 weeks of Ramipril on neurocognitive function in patients with GBM receiving chemoradiotherapy as measured by the Clinical Trial Battery Composite (CTB COMP) score, 3) to estimate the time to neurocognitive decline as assessed by the Clinical Trial Battery Composite (CTB COMP) score, 4) to estimate the effect of treatment on specific non-memory cognitive functions including attention, executive function, visuo-motor skills, working memory, a screening measure of global cognitive function, mood, quality of life, fatigue and sleep disturbance, 5) to collect preliminary

data on the presence of apolipoprotein epsilon (ApoE) isoform 4 serum (peripheral blood lymphocyte) test positivity as measured by quantitative PCR, and 6) To estimate neurocognitive function in surviving patients at the 4 month post RT endpoint. We will also explore differences in 4 month post RT outcomes by whether the patient received Optune® (also known as Tumor-Treating Fields or TTFields) as part of their standard treatment following RT.

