## **12.2 Accrual and Feasibility**

### **Sample Size**

We will assess the dropout rate to inform us regarding the design of a subsequent randomized study. We will test the null hypothesis that retention  $< 65\%$  versus the alternative hypothesis that retention  $\geq 65\%$ , with 90% power for detecting an alternative retention of 80%. The 65% threshold is related to retention rate, and is different from the 75% of doses required for compliance (Section 12.1). Assuming a 1-sided test at the 0.05 significance level, we obtain a sample size of 75 participants. The sample size calculation was conducted using NQuery Advisor v7.0. Based on this calculation, we will plan for a sample size of 75, which will allow us to determine with a high level confidence whether or not the retention rate is sufficient to justify a subsequent study to this pilot.

We will also estimate the effect size in terms of reduction in neurocognitive decline in the intervention group as compared to historical controls. No formal statistical hypothesis will be tested for the purpose of declaring efficacy. The effect size, along with the estimate of the dropout rate, will be used to power and assess the feasibility of a planned subsequent randomized study. We expect an accrual rate of approximately 4 per month based on prior NCORP studies in similar brain tumor populations.

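### Section 12.7 cannot be executed or interpreted as written: toxicity tests with no comparator, no named data source for related grade 3+ toxicity, and a response comparison that cannot rule out tumour protection

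*Combined protocol and SAP*

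**What the plan says.** Section 12.1 fixes the design: "We propose a single arm pilot study to assess the feasibility of the use of Ramipril for GBM". Section 12.7 plans Fisher exact tests for individual toxicities, then a covariate-adjusted logistic regression to "assess treatment differences in the incidence of any grade 3 or higher toxicity possibly, probably or likely related to Ramipril". No comparator is named for either. It closes with: "In order to rule out cytoprotection of tumor by Ramipril, response rates will be compared to historical controls from RTOG 0825".

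Section 10.3 makes three kinds of event reportable: unexpected grade 3 rated possible, probable or definite; unexpected grade 4; and all grade 5. The expected grade 3 and grade 4 cells of its chart are empty at every attribution. This is deliberate: "By not collecting all AEs, we hope to expend our efforts in identifying toxicities that are unexpected and related to Ramipril".

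Toxicity Assessment is a separate item. Section 7.3 says: "Assessments by the study team will be done from Week 1 of RT and the start of Ramipril to 5-month post RT". The Schedule of Events in 7.1 marks it only at Weeks 1-6 and Week 10.

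Section 12.8 leaves tumour response to the treating investigator under local standard of care. Section 4.1.1 requires histology "obtained at the time of a partial or gross total resection of the tumor".

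**The concern.** There are three difficulties.

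1. A test of treatment differences needs a second group, and an outcome defined by attribution to ramipril needs a second group that could have it.
2. The related toxicities most likely to occur are the known ones. Section 6.2 lists hypotension, cough, syncope, abnormal kidney function and raised potassium. If these count as expected, they fall in the cells that Section 10.3 leaves empty. An analysis run from the adverse event form would understate related grade 3-4 toxicity, and the randomised trial that this pilot is meant to inform would inherit that profile.
3. To rule something out needs a stated margin and enough precision. Section 12.7 gives neither a margin nor a test nor a power. A null comparison could be taken as evidence that ramipril does not protect tumour.

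**Working it through.** **The plan's own sample size.** Section 12.2 states: "Assuming a 1-sided test at the 0.05 significance level, we obtain a sample size of 75 participants". Inputs: retention 65% against 80%, 90% power.

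n = [(1.645·√(0.65·0.35) + 1.282·√(0.80·0.20)) / 0.15]² = 74.78, so 75.

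The figure reproduces. Exactly, rejecting at 56 or more of 75 gives alpha 0.0485 and power 0.900. This sizes retention only; nothing in Section 12.7 is sized.

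**1. Toxicity tests.** With no control group, the treatment term is constant and no difference can be estimated. If RTOG 0825 controls (number m, not given in the documents) are used for ramipril-attributed toxicity, their count is zero by definition. With x events in 75 and none in m, the two-sided Fisher p equals C(75, x) / C(75+m, x) in these cases:

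- m = 300, x = 2: (75·74)/(375·374) = 5,550/140,250 = 0.040
- m = 450, x = 2: (75·74)/(525·524) = 5,550/275,100 = 0.020
- m = 150, x = 3: (75·74·73)/(225·224·223) = 405,150/11,239,200 = 0.036

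Two or three events would therefore be significant by construction. The logistic treatment coefficient has no finite maximum likelihood estimate, because one group has no events.

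**2. Data capture, side by side.**

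- Section 12.7 wants all related grade 3+ toxicity. Section 10.3 reports only unexpected related grade 3, unexpected grade 4, and grade 5.
- Sections 5.2 and 5.5.3 require drug-attributed grade 3+ toxicity to be identified at weekly review, with no restriction to unexpected events. Section 12.7 does not name this source. Appendix B lists titration, administration and assessment forms but none named for toxicity.
- Sections 3, 5.2 and 7.3 continue toxicity assessment to 5 months post RT. The schedule stops it at Week 10. Dosing runs to Week 22, so on the schedule 12 of 22 dosing weeks have only the restricted adverse event row.

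If the adverse event form were the source, 0 of 75 would carry an exact 95% upper limit of 1 − 0.025^(1/75) = 4.8%. The documents give no grade 3+ rate. If the true rate of expected related grade 3-4 events were 2%, 5% or 10% (assumed), then 75 × rate = 1.5, 3.75 or 7.5 patients would have one and none would be on that form.

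**3. Response.** The control size and response rate are not given. Assume 200-300 controls, 20-50% response, and equal true rates.

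Half-width = 1.96·√[p(1−p)(1/75 + 1/m)]

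| p | m = 200 | m = 300 |
|---|---|---|
| 20% | 10.6 points | 10.1 points |
| 50% | 13.3 points | 12.7 points |

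The chance that the 95% interval excludes a 10-point loss is Φ(0.10/SE − 1.96). For p = 20%, m = 300, SE = 0.0516, giving 49%. For p = 50%, m = 200, SE = 0.0677, giving 31%. Two-sided power to detect a true 10-point drop from 30% is 35-42% for 150-450 controls.

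**The case against.** The strongest reply is that the data may well exist. Toxicity Assessments are not limited to unexpected events. Section 8.3.1 keeps them for patients off agent, and the monitoring plan in 11.4 lists observed toxicities apart from adverse events. Blood pressure is recorded weekly in RT and at months 1 and 4; creatinine and potassium are measured weekly in RT and at Week 10. A reader might infer that related toxicity cannot be obtained at all. The documents do not support that: the form fields are not shown, so neither capture nor its absence is proven. What stands is that Section 12.7 names no source and the schedule disagrees with the text.

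A reader might also set the 4.8% limit against the 11% hypotension cited in Section 6.1 and infer a hidden signal. The two are not comparable: the 11% has no stated grade, while 4.8% would concern recorded grade 3+ related events.

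RTOG 0825 is the declared comparator in 12.1, and 2.3 records agreed data access. An all-cause toxicity comparison is therefore conceivable if collection rules match. That is not what is written, and it does not rescue the attributed outcome.

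On response, Section 12.4 already promises 95% intervals and pre-specifies extent of resection as a covariate for secondary analyses. Section 12.7 does not say that non-significance is the criterion; that is a risk of misreading, not a stated rule. Nor is a 10-point loss never excludable: the chance is 31-49% under the assumptions above. The share of patients with gross total resection is not given, so the effect of absent measurable disease cannot be sized.

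The attribution wording is minor. Section 10.1.4 has no category *likely*, although it describes Probable in that sense; the omission of Definite looks like a drafting slip, since Section 3 uses all three terms.

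**Conclusion.** The point holds in three parts.

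- The tests of treatment differences in ramipril-attributed toxicity have no valid comparator. This follows from the design and needs no assumption; the Fisher examples assume 150-450 controls.
- The incidence of related grade 3+ toxicity is not assured by the stated capture. The 4.8% limit applies only if the analysis is run from reportable adverse events.
- The response comparison cannot rule out tumour protection. It is non-randomised, locally assessed, in resected patients, with no margin. The 10-13 point half-width rests on assumed control sizes and response rates.

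This is a should-fix. Toxicity is not among the objectives or endpoints in Sections 1 and 8, and neither primary endpoint is affected.

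**What to change.** 1. In 12.7, replace the Fisher and logistic comparisons with single-arm counts and exact 95% intervals, using the Section 10.1.4 terms possible, probable and definite.
2. State that 12.7 draws on the Toxicity Assessments. Record in REDCap, non-expedited, every grade 3+ event with one of those attributions, expected or not. Reconcile the Toxicity Assessment row in 7.1 with 7.3.
3. Replace the claim to rule out tumour protection with an estimated difference in response from RTOG 0825, with a 95% interval and allowance for extent of resection. Add progression or death by month 4 where both data sets allow it. State that non-significance will not be read as absence of tumour protection.

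The cost is an amendment to the 10.3 reporting rules and one schedule row, revised wording in 12.7, and modest extra data entry. Drug-attributed grade 3+ toxicity is already sought weekly during RT, and no patient's treatment changes.

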### 8.2 Secondary Endpoints

**Participant reported outcomes (PRO):** Participant-reported outcomes will complement the neurocognitive battery. The EORTC Quality of Life Questionnaire-Core 30/Brain Cancer Module-20 (EORTCQLQ30/BN20) will measure several domains of functioning (physical, emotional, cognitive, social, fatigue, pain, etc.) (8 minutes). Each cognitive test and PRO proposed has adequate psychometric properties and has been used previously in clinical trials of oncology patients.

**Imaging:** Adequate imaging for diagnostic, treatment planning and follow-up imaging will follow standard of care practices and will include contrast-enhanced T1-weighted MRI and T2 or FLAIR imaging. Contrast-enhanced CT will be allowed only in cases where patients are unable to undergo MRI because of non-compatible devices. MRI of the brain will be performed 1- and 4-month post-RT or until time of tumor progression, should that occur prior to the 4-month post-RT time point. Response assessment will be based on treating investigator assessment and institutional standard of care. Imaging parameters will only be utilized to measure response and progression.

**Other variables to be measured:** Sociodemographic variables to be assessed in a questionnaire at baseline will include age, education, race/ethnicity, menopausal status, co-morbid medical conditions, concomitant medication, marital status, socioeconomic status, tumor size and location. Variables to be assessed after completion of each treatment phase by treating physician include dates, dose and compliance of temozolomide administration, radiation dose, radiation dose per fraction, and radiation volume (e.g. planned treatment volume (PTV)). *Cognitive reserve* (CR) will be measured with the Shipley Scale-Vocabulary with educational (years in school) and occupational attainment (standardized 8-level classification) also measured as proxies for CR.

**Biomarkers:** APOE genotype, a risk factor for cognitive impairment and dementia, will be derived from

whole blood samples taken at baseline at the site of study enrollment. See Section 10.1 for sampling handling and processing.

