Treating physician response rate will be summarized at each timepoint with corresponding 95% confidence intervals. Time to neurocognitive failure will largely follow the method reported in Gilbert *et al.* for evaluating if there is meaningful difference in the risk of cognitive progression. Neurocognitive failure will be defined as the first decline on reliable change index on any of the individual cognitive tests. In the presence of competing risks for neurocognitive failure, including GBM-related mortality risk, we plan to explore the use of competing risks methods for both descriptive statistics (e.g. the Kaplan-Meier curves) and competing risk regression analysis. Competing risk methods are needed because time to neurocognitive failure is not independent of mortality and ignoring events from competing risk will lead to biased results. The competing risk analysis will be based on the method proposed in Gray and Fine and Gray using SAS macro %CIF and PROC PHREG. Patient reported outcomes will be assessed as described above for the CTB COMP.

Exploratory subgroup analyses will be conducted for all 4 month post RT outcomes by whether the patient received Optune® (also known as Tumor-Treating Fields or TTFIELDS) as part of their standard treatment following RT. Differences by Optune® for continuous outcomes will be assessed by two-sample t-tests where parametric assumptions hold; otherwise Mann-Whitney U tests will be applied. For categorical outcomes, Fisher's exact or Chi-square tests will be implemented. Corresponding 95% confidence intervals will also be presented for outcomes within each subgroup.

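### Section 12.7 promises to rule out tumour protection by Ramipril, but with no margin, no interval for the difference and a sample sized for retention, the response comparison cannot reliably exclude a 10-point loss unless response is about 10% or lower

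*Combined protocol and SAP*

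**What the plan says.** Section 12.7 (Evaluation of Toxicity) gives the purpose and the comparator in one sentence: "In order to rule out cytoprotection of tumor by Ramipril, response rates will be compared to historical controls from RTOG 0825". It names no margin, test, confidence level, timepoint or decision rule.

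The other places that bear on it are:

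- Section 12.4: "Treating physician response rate will be summarized at each timepoint with corresponding 95% confidence intervals". These intervals describe this trial's own rate. No interval is planned for the difference from RTOG 0825.
- Section 8.2: "Response assessment will be based on treating investigator assessment and institutional standard of care". Section 12.8 says the same. No response criteria are named.
- Section 12.2, on the sample size: "we obtain a sample size of 75 participants". The calculation concerns retention only ("The 65% threshold is related to retention rate").
- Section 4.1.1 admits patients after partial or gross total resection, so some may have no residual tumour in which response can be seen.
- Section 12.4 says secondary analyses will consider covariate adjustment against the RTOG 0825 cohort. Section 12.7 does not mention it.

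**The concern.** Ruling out is a claim about the worst loss still compatible with the data. It needs a named loss and an interval for the difference whose lower limit is better than that loss. An unspecified comparison supplies neither, and an interval around the single-arm rate does not replace one for the difference. With this few patients, similar-looking or not significantly different rates could be reported as showing no tumour protection when a material loss remained compatible with the data.

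This is the only planned analysis aimed at whether a drug introduced as cytoprotective also protects the tumour. The other reassurance, in sections 2.2 and 6.1, comes from outside this trial. Section 2.3 says the trial will support the design of a larger randomised study, so an unsupported statement on this point could be carried forward.

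**Working it through.** **1. The plan's own figure.** Section 12.2 tests retention of 65% against 80%, one-sided 0.05, 90% power. By the one-sample normal approximation,

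n = [(1.645 × √(0.65 × 0.35) + 1.2816 × √(0.80 × 0.20)) / 0.15]² = [(0.7846 + 0.5126) / 0.15]² = 74.8, so 75.

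An exact check agrees: calling 56 or more of 75 a success has type I error 0.0485 and power 0.900. The figure reproduces, but response plays no part in it.

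**2. Inputs for response.**

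- From the documents: 75 treated patients.
- Assumed: N = 100 to 300 RTOG 0825 controls, with unlimited controls (a fixed benchmark) as the best case; a response rate p of 20 to 50%, with 10% shown for contrast; all 75 evaluable unless stated.
- Illustrative: a 10-point loss, because the plan sets no margin.

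**3. Formulas.** With equal true rates, SE = √[p(1−p)(1/75 + 1/N)]. The 95% half-width is 1.96 × SE. The chance that the lower limit excludes a 10-point loss when there is none is Φ(0.10/SE − 1.96).

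Example with p = 0.30 and N = 300: SE = √(0.21 × 0.016667) = 0.0592. The half-width is 11.6 points. The chance is Φ(1.69 − 1.96) = 39%.

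| Response rate | Half-width in points, N = 100 / 300 / unlimited | Chance of excluding a 10-point loss, N = 100 / 300 / unlimited |
|---|---|---|
| 10% | 9.0 / 7.6 / 6.8 | 59% / 73% / 82% |
| 20% | 12.0 / 10.1 / 9.1 | 37% / 49% / 58% |
| 30% | 13.7 / 11.6 / 10.4 | 30% / 39% / 47% |
| 40% | 14.7 / 12.4 / 11.1 | 27% / 35% / 42% |
| 50% | 15.0 / 12.7 / 11.3 | 26% / 34% / 41% |

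**4. What 75 patients could exclude.** The smallest loss excludable with 80% power is (1.96 + 0.84) × SE. With 300 controls it is 14.5 points at 20% response, 16.6 at 30% and 18.1 at 50%. Eighty per cent power for a 10-point loss is reached only at response rates of about 8% or lower (300 controls) or 11% or lower (fixed benchmark), ignoring the mirror-image very high rates.

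**5. A conventional test when the loss is real.** For a true 10-point loss, SE = √[p_c(1−p_c)/N + p_t(1−p_t)/75], where c is control and t is treated. The miss rate is 1 − Φ(0.10/SE − 1.96).

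- Least favourable, 50% to 40% with N = 100: SE = √(0.0025 + 0.0032) = 0.0755, miss rate 74%.
- Most favourable, 20% to 10% with N = 300: SE = √(0.000533 + 0.0012) = 0.0416, miss rate 33%.

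The range for 100 to 300 controls is therefore 33 to 74%. Starting from a 30% control rate it is 53 to 74%.

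**6. Fewer evaluable patients.** With 50 evaluable (assumed) and the same control numbers and 20 to 50% rates, the half-width is 12 to 17 points and the chance of excluding a 10-point loss is 21 to 37%.

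All these figures count sampling error only. Non-randomised controls and response without named criteria add uncertainty that no interval of this kind contains.

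**The case against.** The strongest reply is that this is one sentence in a pilot. The decision to proceed rests on retention (sections 1.1.1 and 12.2), no stated rule uses response, and the monitoring board sees summaries of secondary measures every six months (section 11.4). All of that is correct and limits the consequence. It does not answer the point: the plan's disclaimers in sections 12.2 and 12.4 concern declaring efficacy, not declaring that a harm is excluded.

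A second reply is that every figure above depends on control data the documents do not give. That also stands. It is why the results are given as ranges, and why no single half-width should be written into the plan from them.

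Two stronger readings are tempting. A reader might infer that the comparison can never exclude a 10-point loss. The numbers do not support this: there is some chance throughout, 58% at 20% response with unlimited controls and 59 to 82% at 10% response, although excluding a 10-point loss from a 10% rate says little. A reader might also infer that the plan treats a non-significant test as proof of no tumour protection. Section 12.7 specifies no test for this comparison, so that is a risk left open by the wording, not something the plan states. Carry-over into a later trial's consent form is likewise conjecture.

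**Conclusion.** The point holds in a limited form. Section 12.7 claims an inferential property that the design does not have: there is no margin, no interval for the difference, and a sample size derived for another endpoint. The comparison cannot reliably exclude a 10-point loss of response unless the response rate is about 10% or lower.

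Under the assumptions of 100 to 300 controls, 20 to 50% response and 75 evaluable, exclusion is at best about an even chance. It is only somewhat better than even in the most favourable case with unlimited controls. The wording defect does not depend on those assumptions; the size of the shortfall does. It should be corrected before the analysis, but it does not affect the retention objective.

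**What to change.** In section 12.7:

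- Replace the opening words that promise to rule out tumour protection with *To estimate any effect on tumour response*.
- Report the Ramipril minus RTOG 0825 difference in response rate with its 95% confidence interval, applying the covariate adjustment that section 12.4 plans for secondary analyses where the data allow.
- State that only losses beyond the interval's lower limit are excluded, and that a non-significant difference will not be described as absence of tumour protection.
- Compute the expected half-width from the actual RTOG 0825 control number and response rate and the number evaluable here. Do not fix it at 10 to 15 points.

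No new endpoint is needed. In particular, a progression-or-death comparison should not be added for this purpose, because its comparability with RTOG 0825 is not shown.

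The cost is plan wording and one tabulation. Treating-physician response is already captured for each scan, and section 2.3 says access to RTOG 0825 data has been agreed. That section describes the data mainly in neurocognitive terms, so it should be confirmed that control-arm response is included. The downside is that the stated safety claim becomes weaker.
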